A feasibility randomised controlled trial on the efficacy of the WHO's 'Caregiver Skills Training programme'

Statistical Analysis Plan

ISRCTN: 58638141

Description of the trial

This study will assess the feasibility of a randomised controlled trial (RCT) with a 1:1 allocation ratio to a Caregiver Skills Training (CST) intervention group and a control group. The CST intervention is composed of multiple components delivered over a period of approximately 4 months: 9 Group Sessions, 3 Virtual Home Visits, and 4 Telephone Calls over the course of the intervention period. Families will be enrolled in 4 blocks of 20 caregivers in each block, for a total of 80 families. Half will be randomized to receive the intervention and the other half in the control group. Families in the control group will be offered intervention after a waiting period that corresponds to the completion time of the CST programme.

Research objectives

The overall aim of the study is to examine the extent to which the Caregiver Skills Training (CST) programme trial can be feasibly implemented in the study setting. Specifically, we aim to fulfil the following objectives:

Primary objective:

[figure not shown]
• Feasibility and adherence: obtain estimates of participant recruitment and retention rates, data completeness/adequacy, and intervention adherence.

Secondary objectives:

 Obtain preliminary effect estimates of CST on caregiver-child interaction, child language, child emotional and behavioural problems, caregiver distress and caregiver empowerment to power a future large-scale trial.

Trial design

Figure 1 shows the trial flowchart with various stages of the trial and Table 1 details the assessment tools used in each stage. REDCap system will be used to support data capture and monitoring forms for questionnaires, direct assessments, and delivery of the intervention.

Page 3 of 10

Table 1: Assessment tools with time of collection and variables specified for summary/analysis in SAP

summary/analysis in SAP Measure	Enrolment	Baseline	Interventio	Follow-up	Variable extracted
CST Screening Form	х				 Number of sites referring to the study Number of caregivers referred by each site Number & proportion of caregivers eligible Child chronological age
CST Consent Form for Caregivers	х				Number & proportion of caregivers consented
Randomization Form	х				Number of participants randomised by trial arm
Withdrawal Form	x	Х	Х	Х	Number of participants who withdraw
Family Background					Child Biological sex
Information Questionnaire	Х				Language exposure
(FBIQ)					Family income
Children in Family Questionnaire (CFQ)	х				Number of siblings
Social Communication Questionnaire (SCQ)		Х			Total Social Communication Score
Adaptive Behavior Assessment System 3 rd ed (ABAS)		Х			General Adaptive Composite (GAC) score
Resource Use Questionnaire for Preschoolers (RUQ-P)				Х	-
Caregiver-child Interaction Assessment (coded with the Dyadic Communication Measure for Autism (DCMA)		х		х	Frequency completedParental synchronyChild initiations
Distress Thermometer		Х		Х	Frequency completedCaregiver distress
Family Empowerment Scale		Х		Х	Frequency completedFamily subscale total score
Strengths & Difficulties Questionnaire (SDQ)		Х		Х	 Frequency completed Total difficulty score
MacArthur Communicative Development Inventories (MCDI)		х		Х	 Frequency completed Total number of words produced
CST Consent Form for Interventionists	х				-
MT Feedback Form			Х		 Number/proportion of participants attending all 9 Group Sessions Average number of Group Sessions attended

CST Remote Home Visit Guide	х	 Number and proportion of CST participants completing all 3 Virtual Home Visits Average number of Virtual Home Visits attended
CST Telephone Calls Guide	Х	 Number and proportion of CST participants completing all 4 Telephone Calls Average number of Telephone Calls completed
CST Adult-Child Interaction Fidelity Rating	Х	Total fidelity rating score
CST Caregiver Diary	Х	-

Referral: Participants will be recruited from one of five sites across Canada (McGill University Health Centre, Douglas Mental Health University Institute, Autism Yukon, Autism Services of Saskatoon, and South Asian Autism Awareness Centre). Referring professionals at recruitment sites will identify potential participants and present families with a flyer about CST. Registries and other recruitment methods may be also used. Potentially eligible participants will receive a link to complete the CST Referral form to consent for contact by the research team.

Enrolment: The research team will provide consent forms and study information flyers to potential participants either electronically or by mail and assess eligibility. A Screening form will be used to assess the following **Eligibility criteria:**

- 1. The child is aged between 2 to 7 years; 11 months,
- 2. The child is suspected of or diagnosed with ASD, a global developmental delay, an intellectual disability, or any other related neurodevelopmental condition,
- 3. The child is either pre-verbal or has language abilities that are lower than what is expected for their age, i.e., no more than 3 words in length,
- 4. The primary caregiver, i.e., the individual responsible for the daily care and upbringing of the child, including parents, grandparents, or any other adult over the age of 18, can attend all relevant assessment and intervention activities.

Participants will be excluded if they meet any of the following:

- 1. Child is already enrolled in an intensive treatment program (more than 14 hours a week)
- 2. Any factor interfering with the caregiver's ability to complete the program; for example, limited knowledge of English; limited or unstable contact with the child; no access to a computer, tablet or laptop, or a secure internet connection.

Eligible caregivers will be consented to their own and their child's participation in the study. A number of demographic and clinical characterization measures outlined in Table 1 will be collected.

Baseline: Once a block of 20 families have been consented, 10 families will be randomised to receive the CST Programme right away and 10 will be randomized to a wait-list control (treatment as usual). Enrolled participants will complete the measures outlined in Table 1.

Allocation: Once eligible participants have consented, caregiver-child dyads will be randomly allocated to either the immediate CST or control group with a 1:1 ratio and stratified by preferred language (English vs. French in the Quebec sites). Simple randomisation will be performed using random numbers programmes in R-CRAN (version 3.3.0) by an assigned team member who is not involved in the study in any other capacity.

The numbers generated and the randomisation will only be accessible to this team member to ensure concealment. The randomisation procedure will begin once all the families for each block have been recruited.

Participants in the intervention group will receive the CST intervention immediately following enrolment (9 group sessions, 3 home sessions, 4 phone calls). At that time, the waitlist control group will only have access to CST intervention materials, namely the Participant Booklets then wait to receive the full interventions 4-5 months after randomization. Trained interventionists who will offer CST to participating families (called Master Trainers) will also read and sign a consent form to be returned to the research team either electronically or by mail. A number of measures will be collected by the Master Trainers and by the research team to examine intervention adherence and fidelity of interventionists while they deliver CST to both the experimental and control groups.

Follow-up: After the first group of 10 families allocated to the intervention have completed the intervention, all 20 families will undergo follow-up assessments as outlined in Table 1.

Blinding: Due to the nature of the intervention, neither the interventionists nor the families can be blinded to allocation. Every effort will be made to ensure that outcome measures are administered by the research team who are not involved in the intervention delivery and are blinded to treatment allocation. The research team will enter data directly into the online data collection platform to ensure that data monitoring can occur without unblinding. Group assignment will not be revealed until the end of the study after database lock.

Sample size estimation

In line with guidance on feasibility studies, no power calculation has been carried out (Arian et al., 2010). A sample size of 60 to 100 has been shown to be sufficient in a feasibility trial (Moher et al., 2001). A target sample size of 80 (N=40/arm) will be enrolled and randomised based on the practical number of participants who can be recruited to undergo the CST programme at each recruitment site considering the available resources at each recruitment site.

Data monitoring

After the completion of the first programming block, a brief data check will be conducted by an independent analyst. The analyst will request pooled data extracts (no information on participant treatment allocation) to analyse and report the following:

- Summary of numbers initiating the enrolment/intake stage, consented, completing baseline, randomised, and those completing follow up
- Descriptive statistics for baseline demographic measures
 - Frequency and proportion of missing data for demographic variables
- Descriptive statistics at baseline and follow up for caregiver-child outcomes
 - Frequency and proportion of missing data for each measure at both timepoints

Descriptive statistics for baseline demographic measures will be produced for the set of those randomised. By request of the trial team, demographics for all those considered screened will also be summarised descriptively.

Statistical analysis plan

Demographic and clinical characteristics

To describe the study sample and check that the trial arms are balanced, demographic and baseline variables will be summarised by trial arm and across the total study sample. The following variables will be extracted from the Enrolment measures (Table 1):

- Child chronological age (continuous)
- Child Biological sex (categorical: male, female, or intersex)
- Language exposure (mean exposure to testing language at home and school, two items item scored 1 = very rarely to 5=always)
- Family income (binary: Below \$60k average household income versus above)
- Number of siblings (continuous)
- Total Social Communication Score (continuous)
- General Adaptive Composite (GAC) score (continuous)

Summary statistics will be calculated (means and standard deviations for continuous outcomes if normally distributed, medians and quartiles if skewed; frequencies and proportions for discrete outcomes). The randomisation of intervention groups to participants should have ensured that any imbalance over all measured and unmeasured baseline characteristics is due to chance. Therefore, no significance testing will be conducted to assess evidence of group differences for these baseline variables (Teare et al, 2014).

Primary objective: Feasibility and Intervention Adherence

To fulfil the study objectives outlined above, participant flow will be extracted and summarized in Figure 1. The following outcome variables will be included as they relate to feasibility and intervention adherence. Specifically, the following variables will be extracted: *Recruitment and retention rate*

- Number of community partner sites referring to the study
- Number of caregivers referred by each participating site
- Number and proportion of caregivers deemed eligible out of those that initiated the enrolment/intake stage
- Number and proportion of caregivers consenting to participate out of those found eligible overall by each participating site
- Number of participants randomised overall and by trial arm
- Number of participants withdrawing overall and by trial arm

Data completeness/adequacy

- Number of participants completing the Baseline assessment
- Number of participants completing the Follow-up assessment overall and by trial arm

Intervention adherence (by trial arm):

- Number and proportion of CST arm participants attending all 9 Group Sessions, all 3
 Virtual Home Visits, and all 4 Telephone Calls
- Average number and standard deviation of Group Sessions attended, Virtual Home Visits completed, and Telephone Calls completed

Secondary Objective: CST Effect Estimates

Caregiver-child outcome variables

We will estimate preliminary CST effect sizes on the following outcomes collected at Baseline and Follow-up:

- Caregiver-child interactions will be assessed by blinded raters of caregiver-child interactions using the Dyadic Communication Measure for Autism (DCMA; Hurdry, 2013). Specifically, parent Synchrony, calculated as the proportion of all Caregiver communication acts (i.e., the total number of Synchronous, Asynchronous, and Other acts) which are Synchronous, and Child Initiation, calculated as the proportion of all Child acts that are Child Initiations, will be used.
- Caregiver distress will be assessed using the Distress Thermometer as a single-item rated by the caregiver on a 10-point Likert scale from 0 (no distress) to 10 (extreme distress).
- Family empowerment will be measured using the Family Empowerment Scale, a 34item rating scale with 3 subscales (Family, Service System, and Community).
 Specifically, the 12-item Family subscale total score will be used.
- Child emotional and behavioural problems will be measured using the Strengths and Difficulties Questionnaire, a 25-item scale consisting of 5 problem scales. A total difficulty score calculated from 4 out of the 5 problem scales and the total impact subscale, will be used.
- Child language will be assessed using the MacArthur Communicative Development Inventories administered in the preferred language (English or French). Specifically, the total number of words produced (Part I-A) will be used.

Data analysis will be done in Stata (Version 17.0 or higher). Distributional assumptions for regression models will be checked using visual methods (i.e. plots of residuals to check if residuals are normally distributed, scatterplots of standardised residuals to check homoscedasticity) and nonparametric approaches used where necessary.

Preliminary effect estimates for CST outcomes will be produced along with 95% CIs and p-values but treated as exploratory. Outcomes will be analysed using multivariable linear regression analysis. Continuous outcomes will be modelled using linear regression, with post-intervention score predicted by the following (fixed effects): treatment (CST or control), stratifier (French or English), and baseline measurements of continuous outcomes. Mean differences with 95% confidence intervals in continuous outcomes between trial arms will be reported. Other ad-hoc analyses may be requested by the trial clinical team.

Adverse event reporting

No information on adverse events will be collected.

Loss to follow-up and other missing data

The number and proportion withdrawing and lost to follow-up will be summarised overall and by trial arm. If reasons for withdrawal have been captured, these will be summarised overall and by trial arm. The number and proportion of participants missing each measure will be summarised overall, as well as in each arm and at each time point as appropriate.

Missing data will be assessed for randomness, and if missing values were missing completely at random, appropriate methods such as imputation using the overall sample mean will be considered. Since this is a feasibility study, we will not make inferential conclusions about differences between arms. Where appropriate, 95% CIs will be reported. P-values may be reported but will be treated as exploratory. There are no significance thresholds for secondary outcomes.

For individual scales, we will use published guidance on how to handle missing values. If such guidance is not available, scales may be pro-rated for an individual if 20% or fewer items are missing and pro-rating is appropriate. If there are more than 20% missing items, the scale score will not be calculated and will be missing.

Missing baseline data should be limited as participants are ideally not randomised before completion of pre-randomisation measures. If there are missing items at baseline for secondary outcomes, appropriate imputation methods may be applied (i.e. mean imputation; White and Thompson (2015). The research team will make every effort to minimise missing data at follow-up. If there is a considerable amount of missing values in secondary outcomes (>15% missingness), baseline predictors of missingness will be investigated. Baseline variables found to predict missingness in secondary outcomes will be included in adjusted regression models for secondary outcomes to make the missing at random assumption more plausible.

References

- White IR, Thompson SG (2005). Adjusting for partially missing baseline measurements in randomized trials. Stat Med, 15;24(7):993-1007.

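### Effect estimates from 40 families per arm are too imprecise to set the planning difference for a future trial, and the outcome SD and baseline/follow-up correlation are not planned outputs

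*SAP*

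**What the plan says.** Under Research objectives, the secondary objective reads "Obtain preliminary effect estimates of CST on caregiver-child interaction, child language, child emotional and behavioural problems" and continues "caregiver distress and caregiver empowerment to power a future large-scale trial". The effect estimates are the only quantity that the SAP names for that purpose.

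Under Sample size estimation, there is no power calculation and the number is set by practical recruitment: "A target sample size of 80 (N=40/arm) will be enrolled and randomised". The general support offered is "A sample size of 60 to 100 has been shown to be sufficient in a feasibility trial".

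Under Secondary Objective: CST Effect Estimates, each outcome gets a linear regression on arm, language and baseline score. It reports a mean difference with a 95% CI and an exploratory p-value. The model has no term for block or CST group. Under Loss to follow-up and other missing data, the SAP adds "Since this is a feasibility study, we will not make inferential conclusions about differences between arms".

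Descriptive statistics for the outcomes appear only under Data monitoring, in the pooled check after the first block. The final analysis lists neither an outcome SD nor a baseline/follow-up correlation.

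**The concern.** A sample size for a two-arm trial needs a target difference, an SD and, with baseline adjustment, a correlation. A study of this size says little about the first and a fair amount about the other two. The SAP ties the planning purpose to the first and does not list the others.

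If the estimate is high by chance, the later trial is underpowered. If it is low by chance, a worthwhile trial becomes very large or is not run. Required n varies with the inverse square of the effect, so moderate error in the effect becomes large error in n.

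**Working it through.** **Inputs from the SAP.** Four blocks of 20 families (Description of the trial), 1:1 allocation (Allocation), 40 per arm (Sample size estimation), and ten families per block starting CST together (Baseline).

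**Assumed, because the SAP gives no values.** True standardised effect d of 0.3, 0.4 or 0.5; baseline/follow-up correlation r of 0, 0.5 or 0.6; later trial at two-sided 5% and 90% power. Evaluable families per arm are 40, or 40 × 0.85 = 34. The 15% in the SAP is a trigger for investigating missingness, not an expected loss; I use it only as an illustration.

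**1. The plan's own figure.** 4 × 20 = 80, or 40 per arm, which agrees. There is no effect, SD or power to check behind it.

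**2. Precision of the effect.** SE = √[(2/n)(1 − r²)] in SD units, and the 95% half-width is 1.96 × SE. With n = 40 and r = 0, SE = √0.05 = 0.224 and the half-width is 0.44.

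**3. Chance of an underpowered later trial.** Sized on an estimate e, the later trial has n = 2(1 − r²)(3.2415/e)² per arm, where 3.2415 = 1.960 + 1.2816. Its true power is Φ(3.2415 d/e − 1.96). This is below 80% when e > (3.2415/2.8016)d = 1.157d. Among positive estimates the probability is [1 − Φ(0.157 d/SE)] / Φ(d/SE).

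| Per arm, r | 95% half-width (SD) | d = 0.3 | d = 0.4 | d = 0.5 |
|---|---|---|---|---|
| 40, 0 | 0.44 | 46% | 40% | 37% |
| 40, 0.5 | 0.38 | 43% | 38% | 34% |
| 40, 0.6 | 0.35 | 42% | 37% | 33% |
| 34, 0 | 0.48 | 47% | 42% | 38% |
| 34, 0.5 | 0.41 | 45% | 39% | 36% |
| 34, 0.6 | 0.38 | 43% | 38% | 34% |

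The three right-hand columns give the chance that true power is below 80%. Worked case (40, r = 0.5, d = 0.3): SE = 0.194, 1 − Φ(0.243) = 0.404, Φ(1.549) = 0.939, ratio 0.43. In that case about 6% of studies would also give an estimate at or below zero.

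These figures ignore clustering. If each block forms one CST group of ten (an assumption) and the ICC is 0.05, then at 40 per arm and r = 0.5 the SE is √[0.75 × (1.45/40 + 1/40)] = 0.214. The half-width rises from 0.38 to 0.42.

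**4. The same point as planning numbers (unadjusted, 40 per arm).** An observed effect of 0.3 has 95% CI −0.14 to 0.74. It implies 234 per arm at the estimate, 39 at the upper limit, and no finite number at the lower limit. An observed effect of 0.5 has CI 0.06 to 0.94, implying 85 per arm, with limits of 24 and 5,515.

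**5. What the data determine better.**
- *Pooled SD.* The 95% limits, from chi-square on 80 − 2 = 78 df, are 0.865 and 1.186 times the estimate. Required n varies with the SD squared: 0.865² = 0.75 and 1.186² = 1.41, or −25% to +41%. For a fixed target of 0.3 SD that is 175 to 329 per arm around 234. This is a 95% range, as in step 4, so the two can be compared. With 34 per arm (66 df) the SD limits are 0.855 and 1.205.
- *Correlation.* By Fisher's z with 80 families, r = 0.5 has 95% CI 0.31 to 0.65. The factor 1 − r² is then 0.90 to 0.58 around 0.75, which moves n by about +20% to −23%.

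**6. The ICC.** With four CST groups of ten, an ICC estimate of 0.05 corresponds to F = 1.45/0.95 = 1.53 on 3 and 36 df. The exact 95% CI is −0.06 to 0.67, and the design effect at the upper limit is 1 + 9 × 0.67 ≈ 7.

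**The case against.** The SAP never says that the point estimate will be the planning difference. It calls the estimates preliminary and exploratory and reports intervals, and a careful later team could use them well. The intervals, with the numbers analysed, also let one back-calculate an approximate residual SD, which is what a baseline-adjusted sample size needs. No analysis or conclusion of the present trial changes. All of this is fair, and it limits the severity. It does not remove the point: the written purpose attaches to the effects alone, and an SD recovered indirectly is not a planned output with its own interval.

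A reader might infer more than the document supports:

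- *That the SAP contradicts itself.* The statement that no inferential conclusions will be drawn concerns this study. Planning another trial from its results is not such a conclusion, and doing no power calculation is not a conflict either.
- *That the largest of the six observed effects will be picked.* The SAP describes no such choice.
- *That the ICC is a missing planning estimate.* Step 6 shows that it cannot be usefully estimated here.
- *That the loss rate is missing.* Retention is part of the primary objective, and withdrawal, loss to follow-up and missing measures are to be summarised by arm.

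**Conclusion.** The concern holds in a limited form. Estimates from 40 families per arm, or fewer after loss, are too imprecise to set the planning difference. The 95% half-width is 0.35 to 0.48 SD over the inputs tried. A later trial sized on a positive estimate would have less than 80% true power in 33% to 47% of cases. The effect size, correlation, loss and 90% power are my assumptions, but the conclusion holds in every cell of the table. The pooled SD and the correlation are better determined, though not precise, and the final analysis does not list them.

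The change should be made, because following the objective as written leads to poor planning of the next trial. The primary feasibility objective is unaffected.

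**What to change.** Reword the secondary objective along these lines:

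> Estimate, with 95% CIs, the pooled follow-up SD and the baseline/follow-up correlation of each outcome, together with the retention already planned, to inform the sample size of a future trial. The target difference will be set from a justified important difference, not from the observed effect.

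Then:

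- Add one table to the final analysis with the pooled SD and the correlation for each of the six outcomes, with 95% CIs.
- Plan with an upper confidence limit of the SD. The one-sided 80% limit, for example, is 1.076 times the estimate at 78 df, which raises n by 1.076² − 1 = 16%.
- Keep the mean differences with 95% CIs, and use them only to check whether the data are compatible with the chosen target.
- If an ICC is reported, give it descriptively with its CI and take a planning range from outside sources.

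The cost is SAP wording and one table from data already to be collected. The important difference for each outcome has to be sourced outside this SAP, which states none.

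### The MCDI outcome counts words in the testing language only, and the recorded exposure to that language is left out of its model

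*SAP*

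**What the plan says.** Under *Caregiver-child outcome variables*, the SAP fixes the instrument and its language: "Child language will be assessed using the MacArthur Communicative Development Inventories administered in the preferred language (English or French"). The score follows: "Specifically, the total number of words produced (Part I-A) will be used". No count of words in any other home language is mentioned.

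Under *Demographic and clinical characteristics*, the SAP lists "Language exposure (mean exposure to testing language at home and school, two items item scored 1 = very rarely to 5=always"). Its stated use is descriptive: "demographic and baseline variables will be summarised by trial arm and across the total study sample".

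The regression for continuous outcomes, in the analysis text of the secondary objective, predicts the follow-up score from "treatment (CST or control), stratifier (French or English), and baseline measurements of continuous outcomes". Exposure is not among these terms. The only stated rule that could bring it in is under *Loss to follow-up and other missing data*, once more than 15% of outcome values are missing: "Baseline variables found to predict missingness in secondary outcomes will be included in adjusted regression models for secondary outcomes". That route depends on missingness, not on whether exposure predicts vocabulary. The SAP also allows unspecified ad-hoc analyses.

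**The concern.** A word count in one language depends on how much of that language the child hears. Two children with the same baseline count and the same preferred language can be expected to add testing-language words at different rates if one hears the language all day and the other seldom does. The stratifier separates English from French; it does not separate high from low exposure. Baseline MCDI captures the starting level, but not necessarily the later rate of growth.

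Two separate things follow. First, any variation in growth that exposure explains stays in the residual, which costs precision. Second, the result is labelled child language but measures vocabulary in the testing language, so words gained in another language are not counted. Both matter because the SAP's secondary objective is to produce effect estimates that can power a larger trial.

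**Working it through.** The SAP has no figure to reproduce: it makes no power calculation and gives no MCDI mean, SD or exposure distribution. Everything below except the sample size and the model terms is assumed.

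**Precision**

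- Inputs: n = 80 (*Sample size estimation*), with no loss to follow-up assumed. The planned model has four coefficients (intercept, treatment, stratifier, baseline MCDI), which leaves 80 − 4 = 76 residual degrees of freedom. Adding exposure leaves 75.
- Let r be the partial correlation of exposure with follow-up MCDI, given the planned terms. The standard error (SE) of the treatment effect changes by the factor sqrt((1 − r²) × 76/75).

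| Assumed r | SE ratio | Change in CI width |
|---|---|---|
| 0 | 1.007 | 0.7% wider |
| 0.1 | 1.002 | 0.2% wider |
| 0.2 | 0.986 | 1.4% narrower |
| 0.3 | 0.960 | 4.0% narrower |
| 0.4 | 0.923 | 7.7% narrower |

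The break-even point is r² = 1/76, or r of about 0.11. With 68 children analysed (15% lost), the ratios at r = 0.2, 0.3 and 0.4 are 0.988, 0.961 and 0.924, so the picture is the same.

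**What the covariate does to the estimate**

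An illustrative simulation (3,000 runs, n = 80) set the true all-language effect at 40 words. It took observed words as a share of all words at both visits, with the share rising linearly from 0.2 at exposure 1 to 1.0 at exposure 5. Low-exposure children scored 1 to 2.5 and the others 3.5 to 5.

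| Low-exposure children | Effect and SE, planned model | Effect and SE, exposure added | SE ratio |
|---|---|---|---|
| 0% | 33.7 (9.79) | 33.7 (9.65) | 0.985 |
| 10% | 32.0 (9.80) | 32.1 (9.29) | 0.948 |
| 25% | 28.9 (9.56) | 29.0 (8.67) | 0.906 |
| 40% | 25.9 (9.13) | 25.7 (7.99) | 0.875 |

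The effects match simple arithmetic. The mean share is 0.85 in the higher-exposure group and 0.35 in the low-exposure group. With 25% low, 40 × (0.75 × 0.85 + 0.25 × 0.35) = 29.

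The covariate therefore changes precision and leaves the size of the estimate where it was. The shortfall against 40 comes from scoring one language. The SE ratios favour the covariate, because the simulation made observed words a direct function of exposure.

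**The case against.** Leaving out one baseline variable is an ordinary analyst's choice. Age, adaptive behaviour and social communication scores are also collected and not adjusted for. Baseline MCDI in the same language already does most of the work: in the simulation it cut the SE from about 19–20 to 9–10. The outcome is exploratory, no significance threshold applies, and the language of administration is stated openly. All of this stands, and it keeps the point minor. Exposure differs from the other covariates in that it bears directly on what a single-language count can show, and pre-specifying it is stronger than adding it ad hoc after seeing results.

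On planning, a later trial using the same form in a similar population would need the testing-language effect, not the all-language one. The loss in raw words also overstates the loss of power, because the SD shrinks too. With 25% low exposure, the raw effect is 28.9/40.0 = 0.72 of the all-language effect, but effect over SE is 3.02 (28.9/9.56) against 3.57 (40.0/11.19), a ratio of 0.85. This also stands; the remedy for meaning is a correct label, not a different target.

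A reader might infer three stronger things that the SAP does not support:

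- **That the plan expects rarely exposed children.** It gives no expected proportion. The lowest response anchor and a South Asian autism centre among the sites make low exposure possible. The exclusion example "limited knowledge of English" concerns the caregiver, so it does not rule low exposure out for the child.
- **That omitting exposure biases the comparison of arms.** Randomisation makes any imbalance a matter of chance, which the confidence interval reflects, and exposure is summarised by arm.
- **That the missing-item rule, "If there are more than 20% missing items, the scale score will not be calculated and will be missing", conflicts with the exposure score because one blank item of two is 50%.** The rule is written for individual scales. Nothing shows that it governs this two-item descriptive mean, or that a child outside school has a blank item.

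**Conclusion.** The point holds in a limited form and is minor. The MCDI result is an effect on testing-language vocabulary, and a recorded variable that may predict growth in that vocabulary is absent from the model. The precision gain cannot be sized from the SAP. Assuming a partial correlation of 0.2 to 0.4 and 80 children analysed, the interval narrows by about 1% to 8%; at 0.1 or below nothing is gained and the interval widens by less than 1%. The estimate may understate all-language gains in little-exposed children, by an amount that depends on an exposure distribution the SAP does not give.

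It would be tempting to conclude that adding exposure corrects that understatement. It does not: the covariate addresses precision, and only the reporting label addresses meaning.

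**What to change.** - In the MCDI model, pre-specify the language exposure score as a covariate alongside treatment, stratifier and baseline MCDI. State that the home item alone is used where no school item exists, so that no child is dropped for that reason.
- Report the estimate as an effect on *words produced in the testing language*, with a note that it may understate all-language gains in little-exposed children.
- Optionally, add a sensitivity analysis restricted to children with exposure of 3 or more. It would describe a different population in a smaller sample and should be labelled so.

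The cost is one residual degree of freedom out of 76 (SE ratio 1.007 if exposure proves useless) and a few lines of SAP text. No new data are needed.
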